6.5.6 Electrocardiograms

A 12-lead ECG will be performed at the visits outlined in [Table 1](#). All ECGs should be performed after the participant has been supine for at least 5 minutes. All ECGs performed will be saved as source documents. ECGs will be transmitted electronically to the central ECG laboratory for analysis according to the instructions provided by the laboratory to be centrally read by a cardiologist. The overall interpretation of the clinical significance of the ECG will be determined by the investigator and recorded in the participant's eCRF.

6.5.7 Columbia-Suicide Severity Rating Scale

The C-SSRS is a clinician-rated instrument that reports the severity of both suicidal ideation and behavior. Suicidal ideation is classified on a 5-item scale: 1 (wish to be dead), 2 (nonspecific active suicidal thoughts), 3 (active suicidal ideation with any methods [not plan] without intent to act), 4 (active suicidal ideation with some intent to act, without specific plan), and 5 (active suicidal ideation with specific plan and intent). The C-SSRS also captures information about the intensity of ideation, specifically the frequency, duration, controllability, deterrents, and reasons for the most severe types of ideation. Suicidal behavior is classified on a 5-item scale: 0 (no suicidal behavior), 1 (preparatory acts or behavior), 2 (aborted attempt), 3 (interrupted attempt), and 4 (actual attempt). More than 1 classification can be selected provided they represent separate episodes. For actual attempts only, the actual or potential lethality is classified for the initial, most lethal, and most recent attempts. The C-SSRS will be completed at all study visits. At screening (Visit 1), the C-SSRS will be completed for history of suicidal ideation and suicidal behavior for the participant's lifetime and 6 months prior to screening. At all other visits, the C-SSRS will be completed for ideation and behavior since the previous visit. The C-SSRS will be completed on the eTablet by the investigator or designee with current and valid training in administering the assessment. A participant should not be released from the study center until the results of C-SSRS are reviewed and it is confirmed that the participant is not considered to be at risk. Participants who reply with "yes" to questions 4 or 5 in the suicidal ideation section or "yes" to any question in the suicidal behavior section of the C-SSRS at Visits 3 through 6 must be withdrawn from the study and should receive appropriate follow-up as in routine clinical practice, including the ET Visit 7 and the follow-up Visit 8. These participants must continue to complete their daily eDiary through Visit 8 follow-up.

6.6 Other Study Supplies

The following will be provided by the sponsor or a delegate:

- All supplies needed for blood and urine sampling (central laboratory analysis, urine, and urine dipstick reagent strips)
- All supplies needed for on-site urine pregnancy test
- All supplies needed for PK and future biomedical research sample collections
- Shipping materials for shipment of laboratory samples to central laboratory
- All supplies needed for ECG assessment including ECG machine
- Electronic diaries
- Electronic tablet(s)

6.7 Summary of Methods of Data Collection

An IWRS will be used to randomize participants and manage study intervention inventory. All visit data (ie, non-diary data) for this study will be collected by either on the eTablet or, if conducted remotely ([Attachment 12.4](#)), utilizing a web-portal (eg, questionnaires for PROs) or eCRFs via an electronic data capture system. Source documents will be used at the sites and may include a participant's medical record, hospital charts, clinic charts, the investigator's participant study files, as well as the results of diagnostic tests such as laboratory tests, ECGs, etc.

A centralized clinical laboratory will be used for the analysis of all blood and urine samples and for ECG assessments. Additional information on the collection and handling of samples is detailed in the Lab Procedure Manual.

Participants will use an eDiary daily to record the daily total duration of headache, headache characteristics, associated symptoms, the worst pain severity, and acute medication use both in the screening/baseline period and double-blind treatment period until Visit 7/ET. Training for the eDiary will be provided for qualified participants during the Screening/Baseline Visit (Visit 1).

7. Statistical Procedures

7.1 Analysis Populations

The ITT population will consist of all randomized participants. All efficacy analyses will be performed using the mITT population, consisting of all randomized participants who received at least 1 dose of study intervention, had an evaluable baseline period of eDiary data, and had at least 1 evaluable postbaseline 4-week period (Weeks 1 to 4, 5 to 8, and 9 to 12) of eDiary data during the double-blind treatment period. All safety analyses will be performed using the safety population, consisting of all participants who received at least 1 dose of study intervention.

The primary efficacy analysis population to support filing in Europe for off-treatment estimand (defined in Section 7.4) includes all randomized participants who received at least 1 dose of study intervention, had an evaluable baseline period of eDiary data and had at least 1 evaluable postbaseline 4-week period (Weeks 1 to 4, 5 to 8, 9 to 12) of eDiary data during the study, regardless of whether on study treatment or off study treatment.

7.2 Collection and Derivation of Primary and Secondary Efficacy Assessments

On a daily basis during the 28-day baseline period and throughout the study, participants are to record, into an eDiary, information on the daily total duration of headache, headache specific characteristics and symptoms, the worst pain severity, and use of any acute medication. Participants will be able to report headache data, including absence of headache, for the day of the diary report and for the day immediately prior to the day of the diary report, as long as information reported is for a time subsequent to the participant's most recent report. This is defined as a 1-day "missing-recall" window.

Following randomization on Day 1, there are 4 visits at 2-week intervals, followed by 2 visits at 4-week intervals; altogether encompassing a 12-week double-blind treatment phase of the study and a 4-week follow-up phase. In practice, there may or may not be exact 2-week or 4-week durations between 2 consecutive visits, and the visits might not align with each 28-day period recorded in the eDiary (ie, Weeks 1 to 4, 5 to 8, and 9 to 12, corresponding to Days 1 to 28, 29 to 56, and 57 to 84). Therefore, for data analysis purposes, the number of migraine days during the last 28 days prior to the randomization date, will serve as the baseline, and change from baseline will be calculated for consecutive 28-day periods beginning with the date of the first dose of study intervention.

In order to be randomized, a participant should be in the baseline phase for at least 28 days and must report diary data for at least 20 days (including missing recall) during the 28-day baseline period. If less than 28 days of baseline data are reported, the number of headache days and other such counting variables for baseline will be prorated to standardize the count to a 28-day equivalent. Subsequent to treatment start, the number of headache days will be counted in successive and non-overlapping 4-week (ie, 28-day) windows. Headaches that continue into a subsequent 4-week period will be counted (with recorded severity and duration) as occurring in each period.

If any postbaseline diary window for a participant has at least 14, but less than 28 days, of reported data, the prorated approach will be used. If a participant reports less than 14 days of eDiary data, the participant's observed counts in that particular 28-day diary window will be set to missing for that window. These prorating rules will be applied to all efficacy analyses of diary data unless otherwise stated.

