7.2.3 Additional Efficacy Endpoints

Additional efficacy endpoints for the United States and Europe are provided below. Related analysis will be documented in the statistical analysis plan (SAP).

- $\geq 25\%$, $\geq 30\%$, $\geq 50\%$, $\geq 75\%$, 100% improvement (decrease) in monthly migraine days at Weeks 1 to 4, 5 to 8, and 9 to 12
- $\geq 25\%$, $\geq 30\%$, $\geq 75\%$, 100% improvement (decrease) in 3-month average of monthly migraine days
- Change from baseline in monthly migraine days at Weeks 1 to 4, 5 to 8, and 9 to 12
- Change from baseline in monthly headache days at Weeks 1 to 4, 5 to 8, and 9 to 12
- Change from baseline in monthly cumulative headache hours at Weeks 1 to 4, 5 to 8, 9 to 12, and average across the 12-week treatment period
- Change from baseline in monthly acute medication use days at Weeks 1 to 4, 5 to 8, and 9 to 12
- Change from baseline in monthly triptan use days at Weeks 1 to 4, 5 to 8, 9 to 12, and average across the 12-week treatment period
- Change from baseline in monthly moderate/severe headache days at Weeks 1 to 4, 5 to 8, 9 to 12, and average across the 12-week treatment period
- Change from baseline in monthly severe headache days at Weeks 1 to 4, 5 to 8, 9 to 12, and average across the 12-week treatment period
- Change from baseline in weekly migraine days at Weeks 1-4

- Participant having a migraine day on the day of initial dose and on each day of the 6 days post the initial dose.
- Change from baseline in the HIT-6 total score at Weeks 4, 8, and 16 (for Europe and Canada)
- Change from baseline in the HIT-6 total score at Weeks 4, 8, 12, and 16 (for all regions except Europe and Canada)
- At least a 5-point improvement (decrease) from baseline in HIT-6 total score at Weeks 4, 8, 12, and 16
- Participant assessed by the PGIC as “much better” or “very much better” at Week 12
- Participant reporting “satisfied” or “extremely satisfied” with study medication for migraine prevention at Weeks 4, 8, and 12
- Change from baseline in percent work time missed, percent impairment while working, percent overall impairment, and percent activity impairment due to migraine at Weeks 4, 8, and 12 as assessed by the WPAI:MIGRAINE
- Change from baseline in the MIDAS total score at Week 12
- Change from baseline in MIDAS absenteeism score (Questions 1, 3, and 5) at Week 12
- Change from baseline in MIDAS presenteeism score (Questions 2 and 4) at Week 12
- Change from baseline in PGI-S score at Weeks 4, 8, and 12

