7.5.2 Other Subgroup Analyses

A subgroup analysis by exposure to migraine prevention medication, preventive medication failures, and acute medication overuse is planned for the following efficacy endpoints:

- Change from baseline in mean monthly migraine days across the 12-week treatment period
- Change from baseline in mean monthly headache days across the 12-week treatment period
- Change from baseline in mean monthly acute medication use days across the 12-week treatment period
- At least a 50% reduction in 3-month average of monthly migraine days
- At least a 75% reduction in 3-month average of monthly migraine days
- A 100% reduction in 3-month average of monthly migraine days

If models do not converge, descriptive statistics for subgroups will be provided. Details will be provided in the SAP.

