Table 10.2-3. Analysis of Additional Efficacy Endpoints and Health Outcomes

Assessment/ Term	Endpoint	Timing	Methodology
Monthly migraine days	
 CFB in monthly migraine days 	Weeks 1-4, 5-8, and 9-12	CFB MMRM
	
 ≥ 25%, ≥ 30%, ≥ 50%, ≥ 75%, 100% improvement (decrease) in monthly migraine days 	Weeks 1-4, 5-8, and 9-12	GLMM
	
 ≥ 25%, ≥ 30%, ≥ 75%, 100% improvement (decrease) in monthly migraine days 	Average across the 12-week treatment period	Logistic regression model
Monthly headache days	
 CFB in monthly headache days 	Weeks 1-4, 5-8, and 9-12	CFB MMRM
Monthly cumulative headache hours	
 CFB in monthly cumulative headache hours 	Weeks 1-4, 5-8, and 9-12, and average across the 12-week treatment period	CFB MMRM
Monthly acute medication use days	
 CFB in monthly acute medication use days 	Weeks 1-4, 5-8, and 9-12, and average across the 12-week treatment period	CFB MMRM
Monthly triptan use days	
 CFB in monthly triptan use days 	Weeks 1-4, 5-8, and 9-12, and average across the 12-week treatment period	CFB MMRM
Monthly moderate/severe headache day	
 CFB in monthly moderate/severe headache days 	Weeks 1-4, 5-8, and 9-12, and average across the 12-week treatment period	CFB MMRM
Monthly severe headache days	
 CFB in monthly severe headache days 	Weeks 1-4, 5-8, and 9-12, and average across the 12-week treatment period	CFB MMRM
Weekly migraine days	
 CFB in weekly migraine days 	Week 1-4	CFB MMRM
Migraine day	
 Participants having a migraine day on the day of initial dose and on each day of the 6 days post the initial dose 		Continuous descriptive
AIM-D	
 CFB in monthly Performance Daily Activities domain score at Weeks 1-4, 5-8, and 9-12, and across the 12-week treatment period; CFB in mean monthly Physical Impairment domain score at Weeks 1-4, 5-8, and 9-12, and across the 12-week treatment period; CFB in monthly total score at Weeks 1-4, 5-8, and 9-12, and average across the 12-week treatment period 	Weeks 1-4, 5-8, 9-12, and average across the 12-week treatment period	CFB MMRM

Assessment/ Term	Endpoint	Timing	Methodology

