If a participant reported multiple records on the same day for one specific category ('Today' or 'Yesterday') and records are inconsistent, then the records for that eDiary category on the date with discrepancy will be excluded from endpoint derivation and thus excluded from the analyses. The corresponding records will be flagged in the analysis datasets. If there are duplicated records of daily diary data for the same participant on the same day with the same type, the set of records with the last form access datetime will be used in the analysis because records are duplicated.

The monthly migraine days is defined as the total number of recorded migraine days in the eDiary divided by the total number of days with eDiary records during each monthly period and multiplied by 28. For baseline, a minimum of 20 days' eDiary data during the 4-week baseline period is required for the migraine days to be evaluable. A minimum of 14 days' eDiary data during a postbaseline monthly treatment period is required for the migraine days to be evaluable for that particular period. If a participant does not have at least 14 days of diary data for a monthly treatment period, the migraine days for that period will be considered as missing. Migraine days will be derived for each participant at baseline and for each postbaseline monthly treatment period (Weeks 1-4, 5-8, 9-12). The same method to derive monthly migraine days will be used to derive monthly headache days, monthly acute medication use days, monthly triptan use days, monthly cumulative headache hours, monthly headache day pain intensity, monthly moderate/severe headache days, and monthly severe headache days.

If a participant confirmed that acute medications were taken and entered medications in the eDiary, then the acute medication use day will be set to 'Yes'. If a subject reports 'Yes' to the intake of

allowed medication(s) to treat an acute migraine but does not list any of them in the diary, then the acute medication use days will not be counted in this situation and vice versa.

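### The 100% responder endpoints inherit the diary proration and under-14-day rules: recorded migraine days can drop out of the 3-month version, and unreported days pass as migraine-free in both versions

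*Protocol*

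**What the plan says.** Protocol 7.2 sets two rules for a postbaseline 28-day window. If it "has at least 14, but less than 28 days, of reported data, the prorated approach will be used". If it has fewer than 14 diary days, the "observed counts in that particular 28-day diary window will be set to missing for that window". Their scope is general: "These prorating rules will be applied to all efficacy analyses of diary data unless otherwise stated".

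SAP 16.2.1 gives the formula. Recorded migraine days are "divided by the total number of days with eDiary records during each monthly period and multiplied by 28". With fewer than 14 diary days, "the migraine days for that period will be considered as missing".

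The 100% endpoints come in two forms. Protocol 7.2.3 lists 100% improvement by month, and separately "100% improvement (decrease) in 3-month average of monthly migraine days". SAP 10.2.3 (Table 10.2-3) plans "100% improvement (decrease) in monthly migraine days", by generalized linear mixed model for each month and by logistic regression for the 12-week average. It also plots the proportions by 4-week interval. Protocol 7.5.2 adds "A 100% reduction in 3-month average of monthly migraine days" to its subgroup endpoints. None of these places sets a completeness requirement or an exception.

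Three further provisions matter:
- The mITT population needs only one evaluable postbaseline month (Protocol 7.1, SAP 6.3).
- For the ANCOVA on the 3-month average, the SAP says that no data are missing, because the mean observed on treatment is taken to hold for all 12 weeks (10.2.1.1 and 10.3.2.1).
- The 50% responder analysis uses observed cases without imputation (SAP 10.2.2).

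**The concern.** Proration is a reasonable estimate of a count. At the 100% threshold it behaves differently, because zero scaled up is still zero. Within an evaluable window, an unreported day can hide a migraine day but cannot create one, so the error runs in one direction.

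The under-14-day rule adds a second problem for the 3-month form. It removes a window from the average together with any migraine days recorded in it. A participant can then be reported as having a complete response over 12 weeks while the diary shows otherwise. At stake is whether the reported 100% rates mean what a reader will take them to mean.

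**Working it through.** The documents give no expected rate or power for the 100% endpoints, so there is no planned figure to reproduce.

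**Inputs and formulas**
- Window value: v = 28 × m / d if d ≥ 14, otherwise missing, where m is recorded migraine days and d is diary days (SAP 16.2.1).
- 3-month average: A = mean of the evaluable v. The SAP describes this for the ANCOVA average; applying it to responders is an assumption.
- Reduction: 100 × (B − A) / B. B = 18 is assumed for illustration (the baseline cut point in SAP 12.2). A = 0 gives 100% whatever the baseline.

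**Step 1. Recorded migraine days, 3-month endpoint.** Monthly cells show migraine days / diary days. The last column prorates over all diary days, for comparison only.

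| Case | Month 1 | Month 2 | Month 3 | A | Reduction under the plan | All diary days counted |
|---|---|---|---|---|---|---|
| 1 | 13/13 | 0/14 | 0/14 | 0 | 100% | 28 × 13/41 = 8.88, so 50.7% |
| 2 | 0/14 | 13/13 | 13/13 | 0 | 100% | 28 × 26/40 = 18.2, so −1.1% |
| 3 | 0/28 | 1/13 | none | 0 | 100% | 28 × 1/41 = 0.68, so 96.2% |
| 4 | 1/28 | 0/28 | 0/28 | 0.333 | 98.1% | 28 × 1/84 = 0.33, so 98.1% |

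Cases 1 to 3 are 100% responders with 13, 26 and 1 recorded migraine days. Case 4, with a single migraine day in an evaluable window, is not.

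**Step 2. Recorded migraine days, monthly endpoint.** A window with d < 14 is missing, not a response. With d ≥ 14 and m ≥ 1, v is at least 28 × 1/28 = 1. Recorded days therefore cannot be lost in this way from the monthly endpoint.

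**Step 3. Unreported days, both endpoints.** 28 × 0/14 = 0, so 14 clean diary days score as a 100% reduction for the month. Suppose k of 28 days are truly migraine days and the d reported days are a random subset. The chance of recording none is C(28 − k, d) / C(28, d).

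| True migraine days in the month | 14 of 28 reported | 20 of 28 reported |
|---|---|---|
| 1 | 14/28 = 50.0% | 8/28 = 28.6% |
| 2 | (14 × 13)/(28 × 27) = 24.1% | (8 × 7)/(28 × 27) = 7.4% |
| 3 | 11.1% | 1.7% |

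Over 12 weeks with 42 of 84 days reported, the chance is 50.0% with 1 true migraine day and (42 × 41)/(84 × 83) = 24.7% with 2.

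**The case against.** The strongest reply is that the plan does not define the endpoint as the absence of any migraine day. It is a 100% reduction in monthly migraine days, which SAP 16.2.1 defines as a rate over reported days; zero on that measure meets the definition. This stands as a point about definitions and is why the unreported-days part does not justify a new main rule. It does not answer cases 1 to 3, where the participant's own diary contains migraine days.

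The reply also limits the point in ways that stand:
- A reader might infer that recorded migraine days vanish from every 100% endpoint. Step 2 shows that they do not; only the 3-month form is exposed.
- That exposure depends on averaging evaluable months. The SAP gives no explicit responder formula. If the average were missing whenever a month is missing, the recorded-days problem would not arise.
- A reader might infer a large inflation. In an assumed gamma model (mean 10, SD 6 migraine days per month), the monthly 100% rate is 1.3% with full diaries and 4.9% if everyone reports half the days. That contrast is extreme. If 5% or 10% of participants had half diaries and the rest full ones, the rate would rise by 0.05 × 3.6 = 0.18 or 0.10 × 3.6 = 0.36 percentage points, which is 0.45 or 0.9 of a participant per 250.
- Nothing in the documents suggests widespread half diaries. Entry requires 20 of 28 days (Protocol 4.2), a missed day can be entered the next day (Protocol 7.2), and compliance is reviewed at Visits 2 to 7 (Protocol Table 1).
- A reader might infer bias between arms. That needs diary compliance to differ by arm. The trial is double-dummy blinded (Protocol 5.3), and the documents give no evidence of such a difference.
- The subgroup use appears only in the protocol; SAP 12.2 does not list the 100% endpoint.

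**Conclusion.** The point holds in a limited form. As written, the diary rules reach the 100% endpoints without exception. On the averaging that the SAP describes for its ANCOVA, they allow a 12-week 100% responder whose diary records migraine days. Separately, in both the monthly and the 3-month form, unreported days within evaluable windows can only leave the apparent 100% rate unchanged or raise it.

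The size for the trial cannot be computed, because the documents give neither a diary-completeness distribution nor a 100% responder rate. It is probably small. The probabilities above assume that reported days are a random subset.

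It would be wrong to read this as a threat to the main findings. These are additional endpoints tested at nominal significance (Protocol 7.3.3), outside the multiplicity procedure, so the primary and secondary results are unaffected. The correction is still worth making, because a responder contradicted by the recorded data is hard to defend and easy to prevent.

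**What to change.** In SAP 16.2.1 and 10.2.3, state that any recorded migraine day in Days 1 to 84, including one in a window with fewer than 14 diary days, makes the participant a non-responder for the 3-month 100% endpoint. State the 3-month responder formula in the same place.

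Add a sensitivity analysis of the monthly and 3-month 100% endpoints restricted to participants with near-complete diaries, with the threshold fixed before unblinding. A completeness requirement should not become the main rule: counting everyone without complete diaries as a non-responder would turn dropout and poor compliance into treatment failure. Proration stays as planned for counts and for the 25% to 75% thresholds.

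The cost is a few sentences and a small programming change on data already collected. The reported 100% rates may be slightly lower.
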